### 8 Efficacy

Not applicable.

### 9 Pharmacokinetics

#### 9.1 Pharmacokinetic Parameter Estimation

The PK parameters for KD025 and metabolites KD025m1 and KD025m2 in plasma will be estimated where possible and appropriate for each subject and treatment by non-compartmental analysis methods using Phoenix WinNonlin software (v8.0 or a more recent version, Certara USA, Inc., USA).

#### 9.1.1 Definition of Pharmacokinetic Parameters

Plasma PK parameter definitions are provided in Table 2 for Part 1 primary parameters, in Table 3 for Part 1 secondary parameters, in Table 4 for Part 2 primary parameters and in Table 5 for Part 2 secondary parameters.

# Table 2 Part 1 Primary Plasma Pharmacokinetic Parameters and Rounding Specifications

Parameter	Definition	Unit	DP or SF	No. of DP/SF
Cmax	Maximum observed concentration	mass unit/mL	SF	3
AUC(0-last)	Area under the curve from time zero to the last measurable concentration	mass unit.h/mL	SF	3
AUC(0-inf)	Area under the curve from time zero extrapolated to infinity	mass unit.h/mL	SF	3

SF=significant figures

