KD025 was the main analyte detected in all clinical studies, with maximal plasma concentration (Cmax) ranging from ~100 ng/mL (20 mg once daily [QD] in SLx-2119-09-01) to ~5300 ng/mL (500 mg twice daily [BID] in KD025-102), and median time to maximal plasma concentration (Tmax) ranging from ~2 h to ~8 h. Cmax and the area under the concentration-time curve (AUC) appear to be slightly greater than dose responsive over the 20 to 500 mg QD, but less than dose linear for doses > 500 mg. The half-life typically ranged from 4 h to 8 h, with a few reports greater than 8 h.

Two metabolites, KD025m1 and KD025m2, rapidly appeared in plasma and were readily eliminated. A major metabolite, KD025m2, was detected at Cmax levels ~20% that of parent and AUC approximately 15% that of parent. A minor metabolite, KD025m1, was detected at Cmax levels <5% of parent and AUC ~2% parent. Accumulation of KD025m2 was reported after multiple doses. KD025m1 did not accumulate.

In both Study KD025-105 (a fed/fasted crossover study with KD025 capsules) and Study KD025-106 (a fed/fasted crossover study with KD025 tablets), a high-fat meal given 30 minutes prior to KD025 oral administration had a significant effect on the pharmacokinetics (PK) of KD025. Plasma systemic exposure (Cmax and AUCs) of KD025 was approximately 2- to 3-fold higher under the fed state compared with the fasted state, and the median Tmax value was delayed by 0.5 to 2 h with food.

6 Rationale

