#### 9.1.2 Rules for Pharmacokinetic Parameter Estimation

The imputation of non-numerical or negative values reported in the input dataset will be performed as follows:

- pre-dose sample times will be entered as zero
- values that are below the limit of quantification (BLQ) obtained prior to the Cmax will be entered as zero
- values that are BLQ after the Cmax will be treated as missing
- should partial AUCs be required then values that are BLQ after Cmax may be imputed as zero for these partial areas if lambda-z cannot be determined
- values that are quantifiable after at least 2 consecutive BLQ values after Cmax will be treated as missing for the calculation of PK parameters
- values that are reported as "No Result" (NR) or "No Sample" (NS) etc. will be treated as missing

PK parameters will be estimated using standard Phoenix WinNonlin methods, details of which may be found in the documentation accompanying the WinNonlin software package. The following constraints will apply:

Parameter Estimation	Constraint	
Sampling times	Actual	
Trapezoidal method	Linear up/Log down	
Number of points used for lambda-z	At least 3, not including Cmax	
Minimum requirements for AUC	At least 3 consecutive quantifiable concentrations	
Dose	Nominal	
Rounded dose level	0 decimal places	

Where possible, the terminal elimination rate constant (lambda-z) will be calculated for all subjects. The value of lambda-z will be determined by the slope of the regression line of the natural log transformed concentrations vs time.

The choice of data points for determination of lambda-z will be reviewed by the pharmacokineticist who may adjust the selection in order to provide a more appropriate fit. The choice of data points for determination of lambda-z for each profile will be confirmed following a documented peer review.

Relative Bioavailability (Frel) will be calculated for individual subjects as follows:

$$Frel = \left\{ \frac{AUC \text{ or Cmax (test)}}{AUC \text{ or Cmax (reference)}} \right\} \times 100$$

#### Part 1

Frel will be calculated using Cmax, AUC(0-last) and AUC(0-inf). If for any reason the AUC(0-inf) is not calculable then an alternative AUC over a partial area may be used.

The following Frel comparisons will be made:

- KD025 200 mg QD + itraconazole (Period 2) vs KD025 200 mg QD alone (Period 1)
- KD025 200 mg QD + rabeprazole (Period 3) vs KD025 200 mg QD alone (Period 1)
- KD025 200 mg QD + rifampicin (Period 4) vs KD025 200 mg QD alone (Period 1)

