#### Part 2

....

Frel will be calculated using Cmax(first dose), Cmax(second dose), AUC(0-24), AUC(0-12), AUC(12-24), AUC(0-last) and AUC(0-inf). If for any reason the AUC(0-inf) is not calculable then an alternative AUC over a partial area may be used.

The following Frel comparison will be made:

• KD025 200 mg BID + omeprazole (Period 2) vs KD025 200 mg BID alone (Period 1)

Metabolite to parent ratios (MPR) after a single dose administration will be calculated as follows using Cmax and AUC(0-inf) for Part 1 and Cmax(first dose), Cmax(second dose) and AUC(0-inf) for Part 2. If for any reason the AUC(0-inf) is not calculable then an alternative AUC such as AUC(0-last) or AUC over a partial area may be used:

 $MPR = \frac{AUC \text{ or } Cmax \text{ (metabolite)}}{AUC \text{ or } Cmax \text{ (parent)}} \times \frac{MW \text{ (parent)}}{MW \text{ (metabolite)}}$ 

Reporting and Analysis Plan KD025-107 (QSC200311) Final v2.0 09 Nov 2018 Page 25 of 99

SPS952 T1 v2 RAP Template

Correcting for molecular weight (MW):

- Parent MW = 452.52 g/mole
- KD025m1 MW = 410.44 g/mole
- KD025m2 MW = 411.42 g/mole

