#### 9.2 Pharmacokinetic Parameter Reporting Specifications

The following flags/footnotes may be applied to the PK parameters:

Flag	Footnote	
а	Rsq of regression was <0.9	
b	Period used for regression analysis was less than 2-fold the calculated half-life	
с	Extrapolated portion of AUC(0-inf) >20%	
d	Insufficient post-Cmax data points for estimation of lambda-z	
е	Entire profile BLQ, no pharmacokinetic parameters could be calculated	

In the event that a reliable lambda-z cannot be determined or the extrapolated portion of AUC(0-inf) >20%, then the parameter estimates derived using lambda-z and/or AUC(0-inf) may be deemed unreliable and excluded from the summary statistics and formal statistical analysis.

Additional flags may be applied based on emerging data.

Separate summary tables, figures and listings will be produced for each study part.

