#### 9.2.4 Statistical Analysis of Pharmacokinetic Parameters

Formal statistical analysis will be performed for KD025 and metabolites KD025m1 and KD025m2 PK parameters as follows:

- Part 1: Cmax, AUC(0-last) and AUC(0-inf)
- Part 2:
  - Primary: Cmax(first dose), Cmax(second dose) and AUC(0-24)
  - Secondary: AUC(0-12), AUC(12-24), AUC(0-last) and AUC(0-inf)

The PK parameters will undergo a natural logarithmic transformation and will be analysed using mixed effect modelling techniques. The model will include terms for treatment fitted as a fixed effect and subject fitted as a random effect.

The following pairwise treatment comparisons (test versus reference) are of interest:

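### KD025m1 AUC(0-last) may overstate a large fall in exposure, because each profile ends at its own last quantifiable sample; the size depends on an LLOQ that the documents do not give

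*SAP*

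**What the plan says.** SAP Table 2 defines AUC(0-last), a primary Part 1 parameter, as "Area under the curve from time zero to the last measurable concentration". Under SAP 9.1.2, "values that are BLQ after the Cmax will be treated as missing", the trapezoidal rule is "Linear up/Log down", and an AUC needs "At least 3 consecutive quantifiable concentrations". Nothing makes the two profiles of a test/reference pair end at the same time.

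SAP 9.2.4 applies this to every analyte: "Formal statistical analysis will be performed for KD025 and metabolites KD025m1 and KD025m2 PK parameters as follows". For Part 1 the list is Cmax, AUC(0-last) and AUC(0-inf), each with a geometric mean ratio and 90% CI. AUC(0-12) and AUC(0-24) are secondary parameters in Table 3; they are derived and summarised but not formally compared.

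Protocol 5.3.2 reports: "A minor metabolite, KD025m1, was detected at Cmax levels <5% of parent and AUC ~2% parent". Protocol 6.1 gives a preliminary fall in KD025 exposure of about 80% with rabeprazole. Part 1 samples are 12 h apart after 12 h (12, 24, 36, 48 h).

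Two further rules matter. SAP 9.2 covers weak extrapolation ("In the event that a reliable lambda-z cannot be determined or the extrapolated portion of AUC(0-inf) >20" per cent): such AUC(0-inf) values may be left out of the summaries and the formal analysis. For MPR, the text of 9.1.2 uses Cmax and AUC(0-inf) first, then: "If for any reason the AUC(0-inf) is not calculable then an alternative AUC such as AUC(0-last) or AUC over a partial area may be used". Table 3 nevertheless gives MPR AUC(0-last) its own row.

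**The concern.** KD025m1 is the analyte closest to the assay limit. If its concentrations fall by a large factor in the test period, the last quantifiable sample can move forward, and after 12 h each lost sample removes 12 h of curve. The ratio then divides a short area by a long one and reads too low.

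The parent, at some fifty times the AUC, keeps nearly its whole profile. MPR AUC(0-last) can therefore fall although metabolite formation relative to parent has not changed. In a study meant to separate CYP3A4 effects from gastric-pH effects, that could make a solubility effect look partly metabolic.

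The measure that would correct this, AUC(0-inf), is the one that the 20% rule may remove, and it is more likely to be removed in the same truncated profiles. If fewer than 17 reliable pairs remain, SAP 9.2.4 makes AUC(0-inf) descriptive only. AUC(0-last) would then be the only formally compared KD025m1 AUC in Part 1.

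**Working it through.** The plan gives no figure for this point, so its rules were applied to model profiles.

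**Inputs from the documents**
- Part 1 sampling times, the SAP 9.1.2 rules, and the molecular weights 452.52 (parent) and 410.44 (KD025m1).
- KD025m1 AUC about 2% of parent and parent half-life 4-8 h (Protocol 5.3.2).
- A fall of about 80% (Protocol 6.1), that is, a true ratio of 0.20. This figure is for the parent.

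**Assumptions**
- Parent Cmax at 200 mg of 1000-2000 ng/mL, scaled from the two stated ends: 100 × 200/20 = 1000 and 5300 × 200/500 = 2120.
- LLOQ varied from 0.05 to 5 ng/mL.
- Absorption rate ka of 0.4-1.0/h.
- KD025m1 a constant 2% of parent, with the parent's half-life.
- The same true ratio in all analytes, so the true MPR is 0.02 × 452.52/410.44 = 0.022 in both periods.

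**Worked example** (half-life 6 h, ka 0.8/h, parent Cmax 1000, LLOQ 1 ng/mL)

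C(t) is proportional to exp(-ke·t) - exp(-ka·t), with ke = ln 2/6 = 0.1155/h, scaled to a KD025m1 Cmax of 20 ng/mL.

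1. Reference KD025m1 is 8.10 at 12 h, 2.03 at 24 h and 0.51 at 36 h, so it ends at 24 h. Test values are one fifth of these: 1.62 at 12 h and 0.41 at 24 h, so it ends at 12 h.
2. Reference AUC(0-12) by the SAP's trapezoids is 169.1. The 12-24 h log segment adds 12 × (8.10 - 2.03)/ln(8.10/2.03) = 52.6, so AUC(0-last) = 221.6 after rounding. Test AUC(0-last) = 169.1/5 = 33.8.
3. Reported ratio: 33.8/221.6 = 0.153. Over the common 0-12 h interval: 33.8/169.1 = 0.200.
4. Parent AUC(0-last) runs to 48 h in both periods (11904 and 2381). MPR is (221.6/11904) × 452.52/410.44 = 0.0205, then (33.8/2381) × 452.52/410.44 = 0.0157.
5. AUC(0-inf) gives a ratio of 0.20, but its test value is 29.5% extrapolated, above the 20% limit.

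**Over the grid** (half-life 4, 6, 8 h; ka 0.4, 0.7, 1.0/h; parent Cmax 1000, 1500, 2000; true ratio 0.20)

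| Assumed LLOQ (ng/mL) | Estimable | Median ratio (range) | Median MPR change (range) | Test AUC(0-inf) >20% extrapolated or no terminal slope |
|---|---|---|---|---|
| 0.5, 1, 2, 5 | 99 of 108 | 0.154 (0.057-0.200) | -22% (-71% to +2%) | 64 of 99 |
| 0.1, 0.5, 1 | 81 of 81 | 0.186 (0.117-0.200) | -7% (-42% to +2%) | 20 of 81 |
| 0.05, 0.1, 0.2 | 81 of 81 | 0.197 (0.170-0.200) | -2% (-15% to 0%) | 0 of 81 |

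In the first row the parent ratio stays at 0.187-0.200 over all 108 scenarios. KD025m2, at about 15% of parent AUC, has a median of 0.194 (minimum 0.133).

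A separate set of runs (ka 0.8/h only, LLOQ 0.1-5) found 25 of 27 estimable KD025m1 ratios below 0.20, 2 unaffected and none above. AUC(0-inf) ratios there were 0.196-0.212. At a true ratio of 0.50, 16 of 30 were low (down to 0.337) and 14 were unaffected.

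**The case against.** A reader might infer that the KD025m1 ratio will be too low and that MPR AUC(0-last) will drop. The documents do not support that. They give no LLOQ, no KD025m1 half-life and no KD025m1 figure under rabeprazole. With a sensitive assay, or when both profiles end at the same sample, the bias is small or absent. MPR can stay the same or rise slightly. A faster-cleared metabolite also weakens the effect: with half the parent's half-life (assumed), the medians were 0.178 at LLOQ 0.5-5 and 0.195 at 0.1-1 ng/mL. A median over a chosen grid is not an expected bias. All of this stands, and the point is therefore conditional.

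A reader might also infer that AUC(0-inf) cannot repair the problem. That goes too far. It is formally analysed alongside, was close to the truth in the ka 0.8/h runs, and its exclusion above 20% is discretionary. What remains is that the same truncation makes exclusion more likely.

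Fixed-interval AUCs are already derived and summarised, so the gap is only the missing formal comparison. MPR Cmax does not depend on the last sample. MPR is printed to two decimals, so 0.0205 and 0.0157 both appear as 0.02, although 38 of the 99 scenarios would still print differently. Finally, the no-effect rule in 9.2.4 uses the parent only, and a KD025m1 ratio of 0.15 instead of 0.20 is still a large decrease. These limit the harm to the interpretation of the metabolite results; they do not remove it.

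**Conclusion.** The point holds as a possibility with a known direction. When KD025m1 exposure falls, unequal end times can only lengthen the reference interval relative to the test interval, and no KD025m1 AUC(0-last) ratio in the runs exceeded the truth. For a true ratio of 0.20, the typical reading runs from about 0.15 at an assumed LLOQ of 0.5-5 ng/mL to about 0.197 at 0.05-0.2 ng/mL.

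These sizes rest on the assumed LLOQ, parent Cmax, absorption rate and a constant 2% metabolite level, without between-subject variability. The parent conclusions are essentially untouched. What is at risk is a primary-endpoint metabolite ratio and the reading of MPR. The change is worth making because it is cheap, but no decision rule depends on it.

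**What to change.** In SAP 9.2.4, for KD025m1 and KD025m2 in Part 1, add a test/reference geometric mean ratio and 90% CI over an interval common to both periods, reported beside the standard AUC(0-last). Use the already derived AUC(0-24) or AUC(0-12). When the test profile does not reach that time, use AUC to the earlier of the pair's two last quantifiable times. In the LLOQ 0.5-5 grid the KD025m1 test profile reached 12 h in 72 of 99 scenarios, so the second option will be needed if the assay is not sensitive.

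Where an AUC(0-last)-based MPR is reported, as the Table 3 row or as the 9.1.2 fallback, compute it from metabolite and parent AUC over one common interval, the same in both periods. State the LLOQ, so that the reader can judge how much truncation to expect.

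The cost is SAP wording and a short programming step, with no new data. The downsides are that less of the curve is covered, each metabolite gains one row, and with the earlier-time option the interval differs between subjects. That option is also not perfect: where early samples before Cmax are below the LLOQ and set to zero, its ratio can still be low (minimum 0.143 in the LLOQ 0.5-5 grid, against a true 0.200).

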# Table 3 Part 1 Secondary Plasma Pharmacokinetic Parameters and Rounding Specifications

Parameter	Definition	Unit	DP or SF	No. of DP/SF
Tlag	Time prior to the first measurable (non-zero) concentration	h	DP	2
Tmax	Time of maximum observed concentration	h	DP	2
AUC(0-12)	Area under the concentration vs time curve from time zero to 12 h post-dose	mass unit.h/mL	SF	3
AUC(0-24)	Area under the curve from time zero to 24 h post dose	mass unit.h/mL	SF	3
AUC%extrap	Percentage of AUC(0–inf) extrapolated beyond the last measurable concentration	%	DP	2
T1/2	Apparent elimination half-life	h	DP	2
Lambda-z	Slope of the apparent elimination phase	1/h	DP	4
CL/F	Apparent total body clearance calculated after a single extravascular administration where F (fraction of dose bioavailable) is unknown	mL/min	SF	3
Vd/F	Apparent volume of distribution based on the terminal phase calculated after a single extravascular administration where F (fraction of dose bioavailable) is unknown	L	SF	3
MRT(0-last)	Mean residence time from time zero to the last measurable concentration after extravascular administration	h	DP	2
MRT(0-inf)	Mean residence time extrapolated to infinity after extravascular administration	h	DP	2
Frel Cmax	Relative bioavailability based on Cmax	%	DP	2
Frel AUC(0-last)	Relative bioavailability based on AUC(0-last)	%	DP	2
Frel AUC(0-inf)	Relative bioavailability based on AUC(0-inf)	%	DP	2
MPR Cmax	Metabolite to parent ratio based on Cmax	n/a	DP	2
MPR	Metabolite to parent ratio based on	n/a	DP	2

Reporting and Analysis Plan KD025-107 (QSC200311) Final v2.0

09 Nov 2018 Page 22 of 99

Parameter	Definition	Unit	DP or SF	No. of DP/SF
AUC(0-last)	AUC(0-last)			
MPR AUC(0-inf)	Metabolite to parent ratio based on AUC(0-inf)	n/a	DP	2
Lambda-z Lower*	Lower limit on time for values to be included in the calculation of Lambda-z	h	· DP	2
Lambda-z Upper*	Upper limit on time for values to be included in the calculation of Lambda-z	ħ	DP	2
R  *	Coefficient of determination	n/a	DP	4

DP=decimal places SF=significant figures

\*=these values should be listed but omitted from the descriptive statistics n/a=not applicable

#### Table 4 Part 2 Primary Plasma Pharmacokinetic Parameters and Rounding **Specifications**

Parameter	Definition	Unit	DP or SF	No. of DP/SF
Cmax(first dose)	Maximum observed concentration following the first dose	mass unit/mL	SF	3
Cmax(second dose)	Maximum observed concentration following the second dose	mass unit/mL	SF	3
AUC(0-24)	Area under the curve from time zero to 24 h post dose	mass unit.h/mL	SF	3

SF=significant figures

#### Table 5 Part 2 Secondary Plasma Pharmacokinetic Parameters and Rounding **Specifications**

Parameter	Definition	Unit	DP or SF	No. of DP/SF
Tlag	Time prior to the first measurable h (non-zero) concentration		DP	2
Tmax	Time of maximum observed h concentration		DP	2
AUC(0-12)	Area under the concentration vs time curve from time zero to 12 h post-dose mass unit.h/mL		SF	3
AUC(12-24)	Area under the concentration vs time curve from 12 h to 24 h	mass unit.h/mL	SF	3
AUC(0-last)*	Area under the curve from time zero (i.e. prior to first dose) to the last measurable concentration	mass unit.h/mL	SF	3
AUC(0-inf)**	Area under the curve from time zero (i.e. prior to first dose) extrapolated to infinity	mass unit.h/mL	SF	3
AUCextrap	Percentage of AUC(0–inf) extrapolated beyond the last measurable concentration	%	DP	2
T1/2	Apparent elimination half-life	h	DP	2
Lambda-z	Slope of the apparent elimination phase	1/h	DP	4
MRT(0-last)	Mean residence time from time zero to the last measurable concentration after extravascular administration	h .	DP	2
MRT(0-inf)	Mean residence time extrapolated to infinity after extravascular administration	h	DP	2
Frel Cmax(first dose)	Relative bioavailability based on Cmax(first dose)	%	DP	2

Reporting and Analysis Plan KD025-107 (QSC200311) Final v2.0

09 Nov 2018 Page 23 of 99

Parameter	Definition	Unit	DP or SF	No. of DP/SF
Frel Cmax(second dose)	Relative bioavailability based on Cmax(second dose)	%	DP	2
Frel AUC(0-24)	Relative bioavailability based on AUC(0-24)	%	DP	2
Frel AUC(0-12)	Relative bioavailability based on AUC(0-12)	%	DP	2.
Frel AUC(12-24)	Relative bioavailability based on AUC(12-24)	%	DP	2
Frel AUC(0-last)	Relative bioavailability based on AUC(0-last)	%	DP	2
Frel AUC(0-inf)	Relative bioavailability based on AUC(0-inf)	%	DP	2
MPR Cmax (first dose)	Metabolite to parent ratio based on Cmax(first dose)	n/a	DP	2
MPR Cmax (second dose)	Metabolite to parent ratio based on Cmax(second dose)	n/a	DP	2
MPR AUC(0-last)	Metabolite to parent ratio based on AUC(0-last)	n/a	DP	2
MPR AUC(0-inf)	Metabolite to parent ratio based on AUC(0-inf)	n/a	DP	2
Lambda-z Lower***	Lower limit on time for values to be included in the calculation of Lambda-z	h	DP	2
Lambda-z Upper***	Upper limit on time for values to be included in the calculation of Lambda-z	h	DP.	2
R 2***	Coefficient of determination	n/a	DP	4

DP=decimal places

SF=significant figures

\*=this parameter was referred to as AUC(0-last; first dose) in the protocol

\*\*=this parameter was referred to as AUC(0-inf; first dose) in the protocol

\*\*\*= these values should be listed but omitted from the descriptive statistics

n/a=not applicable

#### 9.1.2 Rules for Pharmacokinetic Parameter Estimation

The imputation of non-numerical or negative values reported in the input dataset will be performed as follows:

- pre-dose sample times will be entered as zero
- values that are below the limit of quantification (BLQ) obtained prior to the Cmax will be entered as zero
- values that are BLQ after the Cmax will be treated as missing
- should partial AUCs be required then values that are BLQ after Cmax may be imputed as zero for these partial areas if lambda-z cannot be determined
- values that are quantifiable after at least 2 consecutive BLQ values after Cmax will be treated as missing for the calculation of PK parameters
- values that are reported as "No Result" (NR) or "No Sample" (NS) etc. will be treated as missing

PK parameters will be estimated using standard Phoenix WinNonlin methods, details of which may be found in the documentation accompanying the WinNonlin software package. The following constraints will apply:

Parameter Estimation	Constraint	
Sampling times	Actual	
Trapezoidal method	Linear up/Log down	
Number of points used for lambda-z	At least 3, not including Cmax	
Minimum requirements for AUC	At least 3 consecutive quantifiable concentrations	
Dose	Nominal	
Rounded dose level	0 decimal places	

Where possible, the terminal elimination rate constant (lambda-z) will be calculated for all subjects. The value of lambda-z will be determined by the slope of the regression line of the natural log transformed concentrations vs time.

The choice of data points for determination of lambda-z will be reviewed by the pharmacokineticist who may adjust the selection in order to provide a more appropriate fit. The choice of data points for determination of lambda-z for each profile will be confirmed following a documented peer review.

Relative Bioavailability (Frel) will be calculated for individual subjects as follows:

$$Frel = \left\{ \frac{AUC \text{ or Cmax (test)}}{AUC \text{ or Cmax (reference)}} \right\} \times 100$$

#### Part 1

Frel will be calculated using Cmax, AUC(0-last) and AUC(0-inf). If for any reason the AUC(0-inf) is not calculable then an alternative AUC over a partial area may be used.

The following Frel comparisons will be made:

- KD025 200 mg QD + itraconazole (Period 2) vs KD025 200 mg QD alone (Period 1)
- KD025 200 mg QD + rabeprazole (Period 3) vs KD025 200 mg QD alone (Period 1)
- KD025 200 mg QD + rifampicin (Period 4) vs KD025 200 mg QD alone (Period 1)

